PROTOCOL

Effect of high vs low dose intravenous dexamethasone on complications in the immediate postoperative phase after periacetabular osteotomy- a randomized, double-blind, controlled trial (DEX-GANZ)

EudraCT number: 2017-000544-17

Approved date: 06.03.2017

Sponsor:

Name: *[name]*
Title: DMSc, consultant

Principal Investigator:

Name: *[name]*
Title: MD, Clinical assistant

Introduction	3
Aim	3
Outcomes	4
Primary outcome	4
Secondary outcomes	4
Methods	5
Study design	5
Randomization	5
Intervention	5
Control	5
Concealment	6
Blinding	6
Time schedule	6
Location	6
Participants	6
Inclusion criteria	6
Exclusion criteria	6
Procedures	7
Inclusion and randomization	7
Standard care procedures	8
Data management	9
Case Report Form	9
Clinical evaluations and outcome registration	9
Other collected data	11
Sample size	11

Introduction

Periacetabular osteotomy (PAO) is the joint-preserving treatment of choice in young adults with symptomatic hip dysplasia.¹ There are currently no studies describing pain in the immediate postoperative period after this procedure, but unpublished data from our institution (the research project “Why in PACU?”) shows that around 70% of patients have moderate to severe pain in the post anaesthesia care unit (PACU). The procedure, involving three osteotomies in otherwise healthy individuals, is likely to produce a substantial surgical stress response, that potentially could be alleviated by multimodal analgesia including high dose glucocorticoids, similar to results from other orthopaedic procedures.^{2,3}

Preoperative low dose glucocorticoids (4-8 mg dexamethasone) are routinely used as a prophylaxis against postoperative nausea and vomiting (PONV).^{4,5} Higher doses (>0.11 mg/kg dexamethasone) have been shown to reduce postoperative pain scores (early and late) and opioid consumption across procedures⁶, and in a meta-analysis of intravenous glucocorticoid versus placebo in total hip arthroplasty (THA), glucocorticoids (8-40 mg of dexamethasone equivalents) were reported to significantly reduce acute pain and total morphine consumption, without increasing complications.⁷

Aim

The aim of this study is to investigate the effect of a single preoperative high-dose steroid injection on complications in the immediate postoperative phase after PAO (primarily pain). Thus, in order to investigate if a high dose of dexamethasone was superior to the low/intermediate dose used routinely for PONV prophylaxis in decreasing immediate pain and other complications after PAO, we conduct a randomised, double-blind trial of 48 mg versus 8 mg of dexamethasone. The primary

hypothesis is that patients who are given 48 mg of dexamethasone (equivalent to approximately 250 mg of methylprednisolone) will be less likely to have moderate or severe pain in the immediate postoperative period (at the operating room and PACU) compared to patients given 8 mg of dexamethasone.

Secondary outcomes include other complications requiring treatment in the immediate postoperative phase (circulatory and respiratory complications, sedation and PONV), length of stay (in PACU and in hospital), readmissions, wound infections, self-reported pain and sleep problems, the first four days after the operation. The investigators hypothesize that patients receiving 48 mg of dexamethasone will have fewer complications and report lower pain scores. The investigators hypothesize that there will be no differences between groups in frequency of wound infections, readmissions or length of stay.

Outcomes

Primary outcome

The proportion of patients reporting moderate to severe pain at rest (>3 out of 10 on a Numeric Rating Scale from 0-10 (NRS)) in the immediate postoperative phase (after extubation in the operating room, and in the PACU until transfer to the ward).

Secondary outcomes

- Differences between groups in average and maximal level of pain in the immediate postoperative phase
- Occurrence of any complications requiring treatment in the PACU (nausea, circulatory or respiratory events)
- Complications/adverse events in the ward the first 24 h
- Length of stay (PACU/Hospital)

- Pain, self-reported. Days 0-4.
- Nausea/vomiting, self-reported. Days 0-4.
- use of opioid and/or antiemetic treatment other than standard, during hospital stay and up to postoperative day 4
- Quality of sleep. Days 0-4.
- Feelings of anxiety, restlessness, fatigue. Days 0-4.
- Any complications (including wound infections) up to 30 days postoperatively days

Methods

Study design

Randomized, double-blind, controlled intervention study. Superiority design.

Randomization

Computer generated, double-blind block randomization. Allocation ratio 1:1, block sizes =8,

unknown to study personnel.

The allocation sequence with intervention details (48 mg or 8 mg dexamethasone) will be concealed in consecutively numbered (1-64), opaque envelopes by two other investigators not otherwise involved in the trial. Before sealing, 20 % of the envelopes are randomly controlled.

Intervention

A single dose of 48 mg dexamethasone iv (Dexamethasone sodium phosphate, Krka, Novo mesto, Slovenia), (12 ml), administered immediately after anesthesia induction, around 30 minutes prior to surgery.

Control

A single dose of 8 mg dexamethasone iv (2 ml) with isotonic saline (10 ml), administered immediately after anesthesia induction, around 30 minutes prior to surgery.

Concealment

The trial drug is contained in a syringe with 12 ml solution, transparent and identical in appearance regardless of dose, labeled with patient identification and handed to trial personnel together with the re-sealed and signed envelopes.

Blinding

Participants, all healthcare providers, trial personnel, data monitoring committee, principal investigator and outcome adjudicators will be blinded throughout the study. After trial completion, the principal investigator receives the allocation sequence without intervention revealed. The intervention allocation will be revealed after performing statistical analysis and drafting the paper, including comments from all authors.

Time schedule

Study expected to start: March 2017

Study expected to finish: August 2019

Location

Copenhagen University Hospital, Rigshospitalet, Denmark. Department of Orthopedic Surgery, and Department of Anesthesiology, Centre of Head and Orthopedics.

Participants

Number of participants: 64, 32 in each group.

Inclusion criteria

- Planned PAO
- Age 18 years or older
- Able to understand Danish or English and to provide informed oral and written consent.

Exclusion criteria

- Previous enrolment in the trial
- Planned simultaneous cheilectomy procedure

- Daily/current use of glucocorticoids or immunosuppressant medication
- Insulin-dependent diabetes
- Pregnancy or lactation
- Allergies to any of the trial drugs.

Procedures

Inclusion and randomization

Eligible patients are informed about the trial in relation to the pre-operative appointment.

Enrolled participants are randomized and assigned to consecutive numbers (1-64) at the morning of surgery.

Standard care procedures

Pre-operative medication	Thromboprophylaxis (low molecular weight heparin) (on the morning of surgery, continued to discharge)
	Acetaminophen 1g (oral, 1-2 hours before surgery)
	Gabapentin 600 mg (oral, 1-2 hours before surgery)
Anaesthesia	
- Induction	Propofol \sim 2 mg kg $^{-1}$ i.v.
- Maintenance	Total intravenous anaesthesia with propofol (5 mg kg $^{-1}$ h $^{-1}$) and remifentanil (25 μ g kg $^{-1}$ h $^{-1}$)*.
- Relaxant	Cicatracurium 0.1 mg kg $^{-1}$ (before skin incision)
- airway	Endotracheal tube. Extubation only after train of four ratio >0.9
Intraoperative fluid therapy/medication	Ringers lactate, 25-30 ml kg $^{-1}$
	Dicloxacillin 2 gram (continued for 24 hours, every 8 th hour)
	Morphine 0.25 mg kg $^{-1}$ (i.v., 45-30 minutes prior to the end of surgery).
	Ondansetron 4 mg (i.v., 30-20 min prior to end of surgery)
Local wound injection	A thin catheter is placed in the wound cavity for injection of local anaesthetics of 0.2% ropivacaine and 0.25 mg epinephrine (100 ml) prior to closure. Every 8 th hour for the first 24 hours after surgery, 20 ml 0.75% ropivacaine and 0.25 mg epinephrine are injected through the catheter.
Post-operative medication	Acetaminophen 1g (oral, 4 times daily, for up to 14 days)
	Ibuprofen 400 mg (oral, 3 times daily, for up to 14 days)
	Oxycodone 10 mg (oral, 2 times daily, for up to 7 days)
	Antiemetics (ondansetron 4 mg) on request
Discharge criteria	Acceptable radiologic control of the hip and clinical control of the wound. Patients should be able to mobilise in and out of bed, walk safely and climb one flight of stairs supported by crutches without other complications hindering discharge.

*However, the dosage could vary depending on indication and decision by the responsible anaesthetist. Data on accurate dosage is collected.

Data management

Before patient enrolment, the trial is approved by the local ethics committee, the Danish data protection agency and the Danish Medicines Agency. The trial will be registered at ClinicalTrials.gov and EudraCT and will be monitored by the Good Clinical Practice unit at a Copenhagen University Hospital.

Data belongs to sponsor.

Case Report Form

Every patient enrolled will have a case report form signed by investigator. REDCap (Research Electronic Data Capture) electronic data capture tools hosted at Rigshospitalet will be used as case report form. Signed informed consent forms will be kept in a separate folder.

Clinical evaluations and outcome registration

Pain (NRS) at rest is evaluated every 15th minute in the PACU. The patient is asked to assign pain a number between 0 (no pain) and 10 (worst pain imaginable). Numbers are transformed into a 4 level-score (NRS 0 = 0 (no pain), NRS 1-3 = 1 (light pain), NRS 4-6 = 2 (moderate pain), NRS 7-10 = 3 (severe pain)). If patients are unable to assign a number (sedation), a verbal rating scale (no/light/moderate/severe pain) is used. Maximal level of pain is defined as the single highest pain score from the time of extubation until PACU discharge to the ward. The average level of pain is calculated for each patient by dividing the cumulated pain scores with the number of measurements from the time of extubation and during PACU stay.

Nausea is evaluated by patients on a four-point NRS (0, none; 1, slight; 2, moderate; 3, severe nausea). Opioid and antiemetic treatment is evaluated through electronic patient records. To allow comparison, opioids are converted into oral morphine equivalents (OMEQs) in mg, using the equianalgesic ratios⁸. Pain, nausea and sedation are assessed from the time of extubation and

every 15 minutes in the operating room, at transfer from the operating room and the PACU and upon arrival at the ward. Side-effects are registered up to 60 hours postoperatively. Adverse events/serious adverse events were defined according to ICH-GCP. Complications requiring treatment during the first 24 hours (including PACU and ward) are defined as; pain requiring opioids, nausea requiring antiemetics, bleeding resulting in transfusion or reoperation, hypotension requiring the use of vasopressors, $>2 \text{ l min}^{-1}$ oxygen supplement or additional lung physiotherapy (CPAP etc.). Complications (any) are registered during hospital stay and up to 30 days postoperatively. Data on potential wound infections were collected from patient records and defined as superficial (involving skin and/or subcutaneous tissue) or deep (involving tissues down to and including the fascia, muscle and bone), based on clinical and microbiological evidence. Hospital length of stay (LOS) is defined as the time (hours and minutes) from start of operation until discharge to home, PACU LOS is defined as the time (hours and minutes) from transfer from the operating room until discharge to the ward. Readmission within the first 30 days are defined as any readmission to hospital.

To explore duration of possible effects and evaluate effect on wellbeing/sleep we include a questionnaire with variables as tertiary outcomes. Self-reported pain and nausea, quality of sleep, presence of fatigue, restlessness, and sadness are investigated by a questionnaire once a day from the day of surgery until the fourth postoperative day. The elements of the questionnaire are; average and worst pain (NRS), average and worst nausea and vomiting (if any), use of analgesics, feelings of sadness, restlessness or fatigue (yes/no), quality of sleep (good, difficulty falling asleep, frequent awakenings, no sleep).

Other collected data

Demographical data (sex, age, height, weight, smoking status, use of alcohol, comorbidities), operative data (date and time of operation, duration of surgery, intraoperative bleeding). Type and dose of medication given by request.

All data are collected from patient record.

Sample size

The estimated sample size for the primary outcome was based on unpublished data from our institution where 70% of patients had moderate and/or severe pain at some point during the PACU stay. We considered a 50% reduction in the proportion of patients with moderate/severe pain from 70% to 35% in the 48 mg vs. 8 mg dexamethasone group clinically relevant. A two-sided significance level of 5% and power of 80% was chosen, with equal allocation to two treatment arms, resulting in the requirement of 32 patients in each arm. As patients were included and randomized at the time of operation, no dropout rate was expected.

3. Kehlet H, Lindberg-Larsen V: High-dose glucocorticoid before hip and knee arthroplasty: To use or not to use—that’s the question. *Acta Orthop* 2018; 89:477–9
4. DREAMS Trial Collaborators and West Midlands Research Collaborative: Dexamethasone versus standard treatment for postoperative nausea and vomiting in gastrointestinal surgery: randomised controlled trial (DREAMS Trial). *BMJ* 2017; 357:1455
5. Oliveira GS De, Castro-Alves LJS, Ahmad S, Kendall MC, McCarthy RJ: Dexamethasone to

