Title: Effect of high vs. low dose intravenous dexamethasone on complications in the immediate postoperative phase after periacetabular osteotomy (DEX-GANZ).

NCT number: NCT03161938

Document date: 16-05-2018

Statistical Analysis Plan

Dichotomous variables are presented as numbers with percentages, and between-group comparisons are assessed with the Fisher exact test. Ordinal variables are presented as median with interquartile range. Continuous variables are assessed for normal distribution with the Shapiro-Wilk test and/or visual examination of histograms and normal QQ-plots. Normally distributed data are presented as mean \pm SD and otherwise as median with interquartile range. Test for significant differences between groups is performed with an independent-samples t-test (normal distribution) or Mann-Whitney U test (non-normal distribution). Data from the questionnaire on PONV and sleep is dichotomized into categories, PONV/no PONV and sleep problems/no sleep problems and assessed as described for dichotomous variables.

Comparison of group differences of pain from the questionnaires is analysed in a two-way ANOVA model (factors being day and group), taking into account the repeated measurements on the same individual (a mixed model with compound symmetric covariance structure).

All available data are used. Missing data mainly occurred in the questionnaires and is assumed to be missing at random. Cases missing all data were ignored (listwise deletion).

Data analyses are conducted using SPSS for Windows, version 25 (IBM Corp., New York, USA) and R for Windows, package version 1.0.153 (R foundation for Statistical Computing, Vienna, Austria) (or newer versions, depending on availability). Author (KS) conducts all analyses, that will be evaluated by [name]. Statistical consultancy will be used for the mixed effects model. All available data are used, missing data is not imputed.

Data processing is done by the investigator, who will continue to be blinded until all results are analyzed, and the abstract is written and accepted by co-authors.

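### The stated 80% power does not hold for the planned test: with 32 per arm and 70% vs 35%, the SAP's Fisher exact test has 76.7% power

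*Protocol*

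**What the plan says.** The primary outcome in the protocol is binary: "The proportion of patients reporting moderate to severe pain at rest", meaning a score above 3 on the 0–10 scale between extubation and transfer to the ward.

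The Sample size section takes its 8 mg rate from unpublished institutional data in which "70% of patients had moderate and/or severe pain at some point during the PACU stay". It treats a halving, "from 70% to 35% in the 48 mg vs. 8 mg dexamethasone group clinically relevant", as the effect to detect. On the error rates it says "A two-sided significance level of 5% and power of 80% was chosen". The arms are of equal size, and the section gives the outcome of the calculation as "resulting in the requirement of 32 patients in each arm". No dropout is allowed for, and no test or formula is named.

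The first paragraph of the SAP covers dichotomous variables as a class: "between-group comparisons are assessed with the Fisher exact test". It names no other test that could apply to the primary outcome, and it contains no power statement of its own.

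**The concern.** The Fisher exact test is conservative in small samples: its actual type I error lies below the nominal 5%, and it loses power as a result. A sample size from an uncorrected normal approximation therefore overstates the power of a Fisher analysis. The protocol gives 32 per arm without a method, and the SAP later commits to Fisher, so it has to be checked whether the 80% applies to the test that will be run.

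What is at stake is how the primary comparison is described. In a 64-patient superiority trial, readers of a non-significant result will look at the stated power to judge how readily the trial could have missed the effect it was designed for. The validity of the test and the conduct of the trial are not in question.

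**Working it through.** **Inputs.** From the protocol's Sample size section: p₁ = 0.70 (8 mg), p₂ = 0.35 (48 mg), difference d = 0.35, two-sided α = 0.05, power 0.80, 1:1 allocation, n = 32 per arm. From the SAP: Fisher exact test. Normal quantiles: z(0.975) = 1.960, z(0.80) = 0.842. Mean proportion p̄ = (0.70 + 0.35)/2 = 0.525, so 2p̄(1 − p̄) = 0.49875. Also p₁(1 − p₁) + p₂(1 − p₂) = 0.21 + 0.2275 = 0.4375.

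**Step 1: reproduce 32 per arm.**

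- Pooled normal approximation, n = [z(0.975)·√(2p̄(1 − p̄)) + z(0.80)·√(p₁(1 − p₁) + p₂(1 − p₂))]² / d² = [1.960 × 0.7062 + 0.842 × 0.6614]² / 0.1225 = 30.75, so 31.
- Average-variance version, n = (1.960 + 0.842)² × 0.49875 / 0.1225 = 31.96, so 32.
- With continuity correction, n = (30.75/4)·[1 + √(1 + 4/(30.75 × 0.35))]² = 36.24, so 37.

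The uncorrected formulas give 31 to 32, and the corrected one gives 37. The protocol's figure therefore fits an uncorrected calculation. The documents do not confirm that one was used.

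**Step 2: approximate power at 32.** The null standard error is √(0.49875/32) = 0.1248 and the alternative standard error is √(0.4375/32) = 0.1169. Power = Φ[(0.35 − 1.960 × 0.1248)/0.1169] = Φ(0.90) = 81.6%. This agrees with the stated 80%.

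**Step 3: exact power of the planned test.** For each of the 33 × 33 possible pairs (x₁, x₂), compute the two-sided Fisher p-value. Then sum Bin(x₁; 32, 0.70) × Bin(x₂; 32, 0.35) over the pairs with p ≤ 0.05.

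| Test, 32 per arm | Power at 70% vs 35% | Maximum type I error |
|---|---|---|
| Fisher exact (SAP) | 76.7% | 3.3% |
| Uncorrected chi-square | 83.9% | 6.0% |

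Defining the two-sided Fisher p-value as twice the one-sided value also gives 76.7%. The shortfall is 80 − 76.7 = 3.3 points, and the chance of missing the effect is 100 − 76.7 = 23.3%.

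**Step 4: sample size at which Fisher reaches 80%.**

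| n per arm | 32 | 33 | 34 | 35 | 36 | 37 |
|---|---|---|---|---|---|---|
| Fisher power | 76.7% | 79.0% | 76.4% | 76.9% | 78.6% | 80.6% |

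Power is not monotone in n because the test is discrete. It first reaches 80% at 37 per arm and is at least 80% at every n from 37 to 60. This matches the continuity-corrected formula. The difference is 2 × 37 − 64 = 10 patients.

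**Step 5: sensitivity to the 8 mg rate.** The Introduction describes that rate only as "around 70% of patients have moderate to severe pain". Keeping the halving and 32 per arm:

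| 8 mg vs 48 mg | Fisher | Normal approximation |
|---|---|---|
| 65% vs 32.5% | 69.6% | 75.1% |
| 70% vs 35% | 76.7% | 81.6% |
| 75% vs 37.5% | 83.1% | 87.5% |

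Most of the vertical spread comes from the assumed rate. The horizontal gap of about 4 to 6 points comes from the choice of test and is present in every row.

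**The case against.** The strongest reply is that the protocol's calculation is not wrong on its own terms. One standard formula gives exactly 32, the protocol never claims that figure for Fisher, and the 80% is a chosen design target. Fisher enters only through a general sentence in an SAP dated 16-05-2018, more than a year after the protocol's approval date of 06.03.2017. This much stands: the discrepancy lies between the two documents and is not a slip inside the sample size paragraph. It does not remove the problem. Matching an uncorrected formula explains how the mismatch arose, and Fisher is the only test the SAP provides for a binary primary outcome.

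A second reply is that 3.3 points is small beside the uncertainty in the 70%. With the same halving, Fisher power is 79.3% at 72% vs 36% and 80.6% at 73% vs 36.5%, so a shift of 3 points in the 8 mg rate closes the gap. That is true, and it is why the shortfall should be called modest. But the rate could as easily be lower, and at the plan's own planning values the stated power is still not the power of the planned test.

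A third reply is that a null result is interpreted mainly from the observed data. That is also fair. It limits the consequence, but it is no reason to leave an incorrect figure in place.

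**Conclusion.** The concern holds. With 32 per arm, 70% vs 35% and a two-sided 5% level, the test in the SAP has 76.7% power, not 80%; reaching 80% would take 37 per arm.

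This rests on reading the SAP's general rule for dichotomous variables as covering the primary outcome, on the protocol's own event rates, and on all 64 patients contributing an outcome, as the protocol expects. The exact power does not depend on which formula the sponsor used; only the explanation of where 32 came from is inferred.

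The effect is confined to the stated power. Type I error stays at or below 3.3%, and nothing in the conduct of the trial has to change.

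**What to change.** Keep 64 patients and keep the Fisher test. In the Sample size section, name the test or formula that produced 32 per arm, and add: *With the planned two-sided Fisher exact test, 32 patients per arm give about 77% power to detect 70% vs 35%.* If sensitivity to the 8 mg rate is reported, give both directions: about 70% power at 65% vs 32.5%, and about 83% at 75% vs 37.5%.

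The cost is one added sentence and a slightly less favourable power figure. Moving to the uncorrected chi-square test to recover the power is not a free alternative, because its type I error can reach 6.0% at this sample size.

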Title: Effect of high vs. low dose intravenous dexamethasone on complications in the immediate postoperative phase after periacetabular osteotomy (DEX-GANZ).

NCT number: NCT03161938

Document date: 16-05-2018

Statistical Analysis Plan

Dichotomous variables are presented as numbers with percentages, and between-group comparisons are assessed with the Fisher exact test. Ordinal variables are presented as median with interquartile range. Continuous variables are assessed for normal distribution with the Shapiro-Wilk test and/or visual examination of histograms and normal QQ-plots. Normally distributed data are presented as mean \pm SD and otherwise as median with interquartile range. Test for significant differences between groups is performed with an independent-samples t-test (normal distribution) or Mann-Whitney U test (non-normal distribution). Data from the questionnaire on PONV and sleep is dichotomized into categories, PONV/no PONV and sleep problems/no sleep problems and assessed as described for dichotomous variables.

Comparison of group differences of pain from the questionnaires is analysed in a two-way ANOVA model (factors being day and group), taking into account the repeated measurements on the same individual (a mixed model with compound symmetric covariance structure).

All available data are used. Missing data mainly occurred in the questionnaires and is assumed to be missing at random. Cases missing all data were ignored (listwise deletion).

Data analyses are conducted using SPSS for Windows, version 25 (IBM Corp., New York, USA) and R for Windows, package version 1.0.153 (R foundation for Statistical Computing, Vienna, Austria) (or newer versions, depending on availability). Author (KS) conducts all analyses, that will be evaluated by [name]. Statistical consultancy will be used for the mixed effects model. All available data are used, missing data is not imputed.

Data processing is done by the investigator, who will continue to be blinded until all results are analyzed, and the abstract is written and accepted by co-authors.
